Official Title: Reducing CV Risk in Prediabetes Patients Using EHR-Based Decision Support

NCT Number: NCT02759055

Document Date: March 5, 2021

PROTOCOL

To improve implementation of evidence-based prediabetes care, a randomized study of the implementation and impact of a prediabetes Clinical Decision Support (CDS) intervention on cardiovascular (CV) risk in prediabetes patients (18-75 years old, body mass index (BMI) ≥25 kg/m², current smoker, uncontrolled blood pressure [BP] or lipids) is justified based on these considerations: (a) over 75% of rural primary care providers (PCP) now use EHR systems²²; (b) in a previous randomized trial, we showed that CDS in primary care clinics significantly improved BP and glucose control in adults with diabetes; (c) this CDS system elicits evidence-informed patient treatment preferences using human-computer interfaces; (d) the CDS system is minimally disruptive of clinic workflow with 80% use rates in targeted diabetes patients and 95% provider satisfaction; and (e) treatment and prioritization algorithms are Web- based and therefore easily updated and highly scalable to any medical group that uses EHRs.

The objective of this project is to systematically and pragmatically improve care and CV risk factors in a population of predominantly rural adult prediabetes patients at high risk for developing diabetes and CV events by implementing aWeb-based CDS system that integrates with local EMR systems and presents the patient and PCP with personalized, evidence-based drug and lifestyle treatment recommendations. To accomplish this objective, we addressed the following specific aims and hypotheses:

Specific Aim 1: Cluster-randomize 34 primary care clinics with 450 PCPs and over 11,000 high-risk adult prediabetes patients to one of two study arms: (a) Usual care (UC) clinics or (b) Intervention (CDS) clinics, which use an EHR-linked, Web-based Prediabetes CDS system designed to improve prediabetes care.

Hypothesis 1 (H1): Relative to those treated at UC clinics, eligible 18 to 75-year-old prediabetes patients at high CV risk treated at CDS clinics will have significantly more favorable trajectories in CV risk estimates over a median 24-month follow up.

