of hypertension with index visit BP ≥140/90 mm Hg or no diagnosis of hypertension but two consecutive BP ≥140/90 mm Hg, or ACC/AHA 10-year CV risk ≥7.5% and LDL either untested or ≥70 mg/dL and not on a statin, (g) no hospice care or chemotherapy for cancer within previous 12 months, and (h) have at least one subsequent primary care visit after the index visit. The patient accrual period (for first index visits) will be 12 months, followed by a 26-month observation period. Thus, patients will have 26 to 38 monthsof follow up, with an expected median of 32 months follow up after the index visit. Pilot data indicate that non- pregnant eligible adults have a median of 6 primary care visits over a 24-month period, ensuring broad inclusion in the analysis. We conservatively estimate an average of 25 eligible patients per consented study PCP with few losses due to death (<1%) in the study period. Few patients switch primary care clinics in Essentia and we accurately match over 98% of patients to a regular PCP. Ultimately, after accounting for all eligibility criteria, we anticipate over 6,600 eligible patients for Aim 1 and Aim 2 analyses. For Aim 1 and Aim 2 analyses we will retrospectively collect CV clinical information and will ask for a waiver of patient consent. The IRB has waived consent in prior and existing evidence-based CDS studies. Patients specifically recruited for focus groups and surveys will be consented and receive

modest compensation for those activities.

Description of Usual Care (UC) and PrediabetesCDS Intervention Conditions.

[figure not shown]
UC Condition. UC clinics and their consented PCPs will have no access to the CDS intervention.

Prediabetes CDS System: The Prediabetes CDS intervention is rooted in a series of antecedent studies that have developed successful forms of CDS for diabetes. The process flow of the intervention is shown in Figure 2.Specific steps in implementation of the Prediabetes CDS intervention are described below.

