Measures of Covariates for Primary and Secondary Analyses: One predictor of CV risk, risk factor, and drug use outcomes is the binary indicator for study condition (CDS or UC). The second key predictor is time elapsed in years between the patient's index visit to each subsequent measurement. Several other measures merit consideration as dependent outcomes, moderators or mediators in primary analyses. These include (a) number of PCP patient encounters, (b) patient characteristics including demographics and pre-intervention clinical values and comorbidities (EHR ICD-10 diagnosis codes and problem lists), and (c) provider characteristics such as age, gender, type of provider, full-time or part-time work status,, specialty board certification status, and proportion of eligible study patients. Patient or provider characteristics may also be used to adjust for covariate imbalance introduced by clinic randomization.

Analysis Plan.

Aim 1 Analytic Approach. Aim 1 pertains to the effectiveness of the Prediabetes CDS intervention, predicting that it will improve the annual rate of change in CV risk (CVR) and individual risk factors relative to UC. Patients age 40-75 at index are included in the Aim 1 analyses because the CDS was programmed to deliver the intervention via treatment recommendations (Figure 2, Step B) to this age group. Rate of change outcomes (e.g., H1, H2) will be tested using random coefficients models in which all available index and post-index outcomes (H1 CV risk, H2 CV risk factors) will be predictedfrom fixed effects for clinic-randomized treatment group, years elapsed since index CVR, the treatment by years elapsed interaction and the index outcome value. Outcomes measured only once per person will follow the same approach, omitting predictors that incorporate years elapsed since index and where warranted including an offset for follow-up time.

Random clinic and patient intercepts will account for clustered observations as appropriate. The link function and error distribution for each model will be determined by the distribution of each outcome. The relationships between years elapsed and CV risk and risk factor outcomes are expected to be linear. The tenability of this assumption will be checked for each outcome and more complex relationships (e.g., non-linear, spline) modeled if warranted.

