The years elapsed parameter will estimate the annual rate of change in CV risk and risk factors among patients in UC clinics in the absence of intervention, while the treatment by years elapsed parameter estimates the difference in the annual rate of change among patients in the CDS relative to UC clinics. It is expected that CV risk will decrease, or increase at a slower rate, among patients in CDS relative to UC clinics. Similar patterns of improvement, or slower worsening, are expected for CV risk factors. Finally, the treatment group parameter is expected to estimate more appropriate pharmacologic use among patients in CDS compared to UC clinics.

2.2.6.1 H1 Sample size justification. We conducted a power analysis to estimate theminimum detectable slope of the treatment by time parameter (power=.80, α_2 =.05) given the anticipated sample size (15 CDS clinics, 7-11 providers per clinic * 25 patients per provider = 2625-4125 CDS patients, 3 CVR per patient).. The patient sample size was divided by the design effect, Neff = N / [1 + (n_{clus} – 1) ρ], to approximate the effective independent patient sample size (Neff) implied by clinic intraclass correlations (ICC) of ρ = .001-.02. The CVR sample sizes (Neff patient * 3 CVR/pt) were divided by the design effect implied by a patient ICC=0.80. The resulting effective CVR sample sizes were used to estimate the minimum detectable standardized linear regression coefficient (β_{CDS}) relative to β_{UC} =0. When ICC_{clin}=0.001, the minimum detectable β_{CDS} =0.044-0.055; when ICC_{clin}=0.005 β_{CDS} =0.061-0.070; and when ICC_{clin}=0.02 β_{CDS} =0.103-0.108.

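### Two of the six minimum detectable effects for H1 (0.044 and 0.061) do not follow from the inputs stated beside them; the same recipe gives 0.046 and 0.0625

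*Combined protocol and SAP*

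**What the plan says.** Section 2.2.6.1 sets power at .80 and alpha at .05 (the subscript 2 read as two-sided) and names the treatment-by-time parameter as its target. Its sample is "15 CDS clinics, 7-11 providers per clinic * 25 patients per provider = 2625-4125 CDS patients, 3 CVR per patient". The patient count is divided by a clinic design effect, 1 + (cluster size - 1) x ICC, for clinic ICCs from .001 to .02. The resulting number of risk scores is then divided by the design effect implied by a patient ICC of 0.80. The last step reads: "The resulting effective CVR sample sizes were used to estimate the minimum detectable standardized linear regression coefficient (β_{CDS}) relative to β_{UC} =0".

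The results are "When ICC_{clin}=0.001, the minimum detectable β_{CDS} =0.044-0.055; when ICC_{clin}=0.005 β_{CDS} =0.061-0.070", followed by 0.103-0.108 at clinic ICC 0.02. In each range the lower number belongs to the larger sample.

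Just above, under Aim 1 Analytic Approach, the plan explains that "the treatment by years elapsed parameter estimates the difference in the annual rate of change among patients in the CDS relative to UC clinics". Section 2.2.6.1 states no UC sample, no split of the clinics between arms, and no standard deviations behind the standardized coefficient.

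**The concern.** The section states every input to the calculation, so the six results should be recoverable. If some are not, either the results or the inputs are misprinted, and a reader cannot tell which. The two values in doubt are the most favourable ones in the section, and both err towards making the design look more sensitive than its stated inputs allow. Because this is the only power statement for H1, it is also where a reader would look to judge what size of difference in risk trajectory the trial could have detected.

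**Working it through.** **Inputs, all from 2.2.6.1**

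- Power 0.80 and two-sided alpha 0.05: 1.9600 + 0.8416 = 2.8016.
- 15 CDS clinics, 25 patients per provider. With 7 providers, 175 patients per clinic and 2,625 in all. With 11 providers, 275 per clinic and 4,125 in all.
- Clinic design effect: 1 + (n - 1) x ICC, with n = 175 or 275.
- Three scores per patient and patient ICC 0.80: 1 + (3 - 1) x 0.80 = 2.6.

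**Formula**

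Effective scores = [N / clinic design effect] x 3 / 2.6. Minimum detectable coefficient = 2.8016 / sqrt(effective scores). The plan does not print this last formula; the matches below support it.

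**Results**

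| Providers | Clinic ICC | Clinic design effect | Effective patients | Effective scores | Recipe | Printed |
|---|---|---|---|---|---|---|
| 7 | 0.001 | 1.174 | 2,235.9 | 2,579.9 | 0.0552 | 0.055 |
| 7 | 0.005 | 1.870 | 1,403.7 | 1,619.7 | 0.0696 | 0.070 |
| 7 | 0.02 | 4.480 | 585.9 | 676.1 | 0.1077 | 0.108 |
| 11 | 0.001 | 1.274 | 3,237.8 | 3,736.0 | **0.0458** | **0.044** |
| 11 | 0.005 | 2.370 | 1,740.5 | 2,008.3 | **0.0625** | **0.061** |
| 11 | 0.02 | 6.480 | 636.6 | 734.5 | 0.1034 | 0.103 |

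Four of the six agree to the printed precision, including all three at 7 providers. The two in bold do not.

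**Can another reading of the same inputs explain the gap?**

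- A Fisher-z calculation gives 0.0458 and 0.0625; an exact noncentral F calculation gives 0.0458 and 0.0624.
- Dropping the -1 from the cluster size gives 0.0459 and 0.0626.
- A one-sided alpha gives 0.0407 and 0.0555 for the two cells, and breaks the 7-provider values (0.049 against 0.055 at ICC 0.001).

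None of these recovers the printed figures.

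**Size of the discrepancy**

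- Power at 0.044: Phi(0.044 x sqrt(3,736.0) - 1.96) = 0.767. At 0.0445, the top of the rounding interval, it is 0.776.
- Power at 0.061: Phi(0.061 x sqrt(2,008.3) - 1.96) = 0.780. At 0.0615 it is 0.787.
- Scores needed for 80% at 0.044: (2.8016 / 0.044)^2 = 4,054, against 3,736, or 8.5% more.
- Scores needed for 80% at 0.061: (2.8016 / 0.061)^2 = 2,109, against 2,008, or 5.0% more.

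**A possible source**

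With 12 providers per clinic (15 x 12 x 25 = 4,500 patients) the recipe gives 0.0443, 0.0614 and 0.1027. These round to the three printed lower ends, 0.044, 0.061 and 0.103. That 12 was used is inference; nothing in the document says so.

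**The case against.** The strongest case for leaving the text alone is that the error is slight. The gaps are 0.0458 - 0.044 = 0.0018 and 0.0625 - 0.061 = 0.0015 in standardized units. They arise only at the larger sample and the two lower ICCs, and both ends of the range at ICC 0.02 are right. The document already reports lack of efficacy, where it explains why the cost-effectiveness hypothesis was dropped, so a recalculation cannot change the design. All of this stands and limits the severity. It does not make the two figures correct.

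A reader might go further in four ways. The documents do not support any of them.

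- *That the calculation is one-arm and ignores sampling error in UC.* Only CDS patients are entered, and a slope difference per SD of time with equal arms would be sqrt(2) = 1.41 times the recipe value. But take a two-arm interaction coefficient that is fully standardized, with equal arms and centred time. The factor sqrt(2) from the second arm is then cancelled by the SD of the product term, which is sqrt(1/2) times that of time, and the recipe value returns exactly. The printed form is therefore compatible with a valid two-arm calculation. Not stating the UC sample, the allocation or the SDs is a reporting gap. Nor is the scale wholly absent, since the text does say that the coefficient is standardized.
- *That the sample conflicts with the rest of the protocol.* Under Study Participants the plan says "we anticipate over 6,600 eligible patients for Aim 1 and Aim 2 analyses". Half of 6,600 is 3,300 per arm. Spread evenly over the 34 clinics of Specific Aim 1, 15 clinics would hold 6,600 x 15/34 = 2,912. Both lie inside 2,625-4,125.
- *That the 2.6 deflator is an error.* It suits a mean better than a within-patient slope, and for a slope it tends to be cautious. The plan offers the design-effect step as an approximation. Aim 1 Analytic Approach names random coefficients models as well as random intercepts and gives no slope variances. The net direction cannot be determined.
- *That the trial is underpowered.* Nothing here shows that.

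**Conclusion.** Wrong as written, minor. Two of the six minimum detectable effects for H1 are inconsistent with the stated 15 clinics, 11 providers, 25 patients per provider, three scores per patient and patient ICC 0.80. The recipe gives 0.046 at clinic ICC 0.001 and 0.0625 at clinic ICC 0.005. The printed values carry about 77% and 78% power, not the stated 80%.

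This rests on reading alpha as two-sided and on the usual normal-theory final step. The four figures that reproduce support both. The finding does not depend on whether the calculation is read as one-arm or two-arm, because it concerns only whether the outputs follow from the inputs.

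**What to change.** Restate the two ranges in 2.2.6.1 as 0.046-0.055 (clinic ICC 0.001) and 0.0625-0.070 (clinic ICC 0.005). Alternatively, if a different upper provider count was used, correct the 7-11 range and the 4,125 so that inputs and results agree.

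In the same edit, add one sentence giving the UC sample and the CDS:UC allocation assumed, and saying what the coefficient is standardized by, since the figures are presented as the treatment-by-time difference.

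The cost is a short recalculation and rewording. If the stated inputs are kept, two figures become slightly less favourable. No extra enrolment and no change to the analysis model is needed.

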Hypothesis 2 (H2): Relative to those treated at UC clinics, eligible 18-75 year-old prediabetes patients with uncontrolled CV risk factors at CDS clinics will have significantly more favorable trajectories in specific CV risk factors, including BP, lipids, smoking, HbA1c, and weight over a median 24-month follow up.

Hypothesis 3 (H3): Relative to those treated at UC clinics, eligible 18 to 75 year-old prediabetes patients at high CV risk treated at CDS clinics will have significantly more favorable patterns of metformin and statinuse over a median 24-month follow up.

Specific Aim 2. Assess the cost of the CDS intervention from the health system (payer) perspective through utilization analyses.

[figure not shown]
Hypothesis 4 (H4): After controlling for demographics and baseline clinical status, eligible patients with prediabetes treated in UC clinics versus CDS clinics will have significantly lower annual healthcare costs from the index date over a median follow up of 24 months.

Specific Aim 3: Describe critical facilitators and barriers for the prediabetes CDS implementation process, outcomes, and future dissemination using a mixed-methods approach.

Note that a previously included cost-effectiveness hypothesis (Hypothesis 5) was not tested due to lack of efficacy of the study intervention. Project results will provide a template for implementation of personalized CDS tools in rural and urban health settings, resulting in more efficient, effective rural healthcare that can be applied across many clinical domains, incorporates patient treatment preferences, and could substantially and sustainably improve the quality of CV care and clinical outcomes of millions of Americans with prediabetes in medically underserved areas.

Overview of Study Implementation Process and Design: The implementation process has four primary components (Figure 1): a) initial organizational engagement; b) adapting and piloting the Prediabetes CDS with Essentia primary care providers and patients; c) a group-randomized controlled study of the adapted CDSin 34 primary care clinics blocked on size and Essentia geographic service area; and d) evaluation of the implementation process and outcomes. It is critical to note that implementation is an iterative process, both in the adaptation

phase and during the randomized controlled trial of implementation and outcomes. Continuous feedback is provided to and

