from organizational leaders, providers, and patients to better understand the facilitators and barriers to implementation and to guide refinements of the CDS.

Group-Randomized Study Eligibility Criteria

Study Sites: The group-randomized controlled study will be implemented in 34 Essentia Health primary care clinics in Minnesota, North Dakota, and Wisconsin. Essentia clinics have used the Epic® EHR since 2004 and have, on average, 14 PCPs (range: 1-56) and 377 prediabetes patients at high CV risk per clinic. Eighty-four percent of the Essentia geographic service area is rural, with 56% of the patient population and 66% of clinics located in this rural area. Average household incomes are less than \$35,000 for 42% of patients, and 45% live in health professional shortage areas.

Study Participants: PCPs and Patients: To participate, PCPs must practice at one of the 34 Essentiaclinics and meet these eligibility criteria: (a) be an adult-care general internist, family physician, non-obstetric nurse practitioner, or physician assistant, and (b) provide ongoing primary care for 15 or more prediabetes adults ages 18-75 with high CV risk. There are currently 441 eligible PCPs which should ensure a more robust understanding of implementation barriers and facilitators in a large PCP community.

To be considered for inclusion in primary or secondary analyses, **patients** must meet all the following eligibility criteria at the time of their indexvisit: (a) be 18-75 years old, (b) have no evidence of diabetes in the previous 12 months (based on lab values, diagnosis codes, use of medications, or on problem list), (c) not be pregnant (d) have the most recent fasting plasma glucose of 100-125 mg/dL or HbA1c 5.7-6.4% within the prior 24 months, (e) have the most recent BMI $\geq 25 \text{ kg/m}^2$, (f) have at least one of the following uncontrolled CV risk factors: current smoking, a diagnosis

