Aim #1- (a) Cardiovascular Risk Trajectories (H1): There is no validated CV risk engine developed with a prediabetes population. Therefore, we propose to use the ACC/AHA 10-year pooled CV risk engine to estimate annual rate of change in CV risk as our primary outcome. We will use the lipid equation for patients with lipid data available to calculate CV risk at the index and all post-index visits and, to minimize missing CV risk values, the BMI equation at the index and all post-index visits for the remaining patients. The BMI equation estimates higher CV risk relative to the lipid equation. Because the calculation method will be consistent across all visits within each patient this difference will not bias the estimated rate of change in CV risk. CV risk scores for each patient will be calculated at each primary care visit from the index through the entire follow-up period using available EHR data elements. As depicted in Figure 2 Step A, at each visit we will search for the most recent data elements, looking back over a period appropriate for each risk component (i.e., 12 months for BP values or medications, DM diagnosis, smoking, BMI; 48 months for lipids). H1 will be supported if the annual rate of change in CV risk scores from the index visit through the end of the follow-up period is lower (ie, less increase) among patients in the CDS relative to UC clinics; (b) Modifiable diabetes and CV risk factors (H2): Risk factors needed to calculate the CV risk scores (weight, systolic blood pressure, HDL-c, LDL-c, totalcholesterol, smoking), are extracted from EHR files as in Figure 2 Step A. H2 will be supported if annual rate of change in CV risk component trajectories are lower among patients in the CDS relative to UC clinics; (c) Metformin and statin use (H3): Data to assess drug treatment are from EHR files such as prescribed medications. The presence or absence of appropriate drug use will be assessed at each visit. H3 will be supported if appropriate drug use improves over the follow-up period among patients in the CDS clinics relative to UC patients.

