Aim #2 – Health Care Costs (H4): Costs for this analysis include intervention costs and incrementalmedical care costs, defined from the health system perspective. Intervention costs include implementation and maintenance and training but exclude research and development costs. Standard accounting methods will be used to measure the cost of the CDS intervention. Medical care costs will include the cost of all prescribed medications and clinic services—including laboratory, lifestyle counseling, and physician services—incurred prior to and up to a 24-month post-index date period by participants in each study group, as indicated by Essentiabilling and clinical encounter data. Reliance on Essentia billing records for measuring medical care utilization may miss costs incurred in other health systems; however, this opportunity is expected to be equal across randomized study arms, and cross-system medical utilization at the clinic level is expected to be limited in this study population. For this reason, though, emergency visits and hospitalizations will be excluded from the analysis—and generally, these events are too infrequent in a sample of this size to accurately predict impact of the study intervention on hospital costs.

While market prices generally are a good estimate of the costs for medical services, the paid amount in this claims system is specific to Essentia at a particular time and may provide a biased view of costs between pre- and post-intervention periods. To address this, we will use Total Care Relative Resource ValuesTM (TCRRVs), which are a nationally standardized set of measures that have been endorsed by the National Quality Forum and are derived from Centers for Medicare and Medicaid Services (CMS) relative value units

(RVUs). TCRRVs extend CMS RVU measures to include utilization categories, such as laboratory services and medications, which do not have CMS RVU weights. Specifically, TCCRVs defined during the midpoint of patient accrual and follow-up (e.g., 2019) will be used to convert claims to represent U.S. dollars.

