Aim 2 Analytic Approach : Incremental medical costs will be estimated using standard health econometric methods. A generalized estimating equation (typically assuming a gammadistribution and log link function) will be used to estimate annualized costs by study arm while allowing clustering by clinicand controlling for demographics, time, and baseline clinical risk factors. The marginal effect of being assigned to an intervention clinic will provide an estimate of the incremental medical cost associated with the CDS intervention. The estimates assume that the CDS is implemented in a large health system with an EHR capable of exporting data to Web-based clinical algorithms. Aim 3 Analytic Approach: For measures not addressed in Specific Aim #1 and #2, measures of centrality will be computed for each of the RE-AIM measures. As an example, 24month CDS use rates will be determined to assess the completeness of implementation. Mixed models will assess changes in patient- and provider-reported outcomes using the Aim 1 analytic approach, with distributional and model modifications made as appropriate to each outcome. For patient and provider experience survey metrics we will describe the proportion of respondents indicating highest satisfaction for specific items at each time point and change over time for these items and for composite scales. Spearman correlations will be used to examine relationships between items, scales, and other study outcomes. Information first will be extracted and orchestrated into categories, themes, and patterns that emerge from and are grounded in data. Coding schemes will be developed and tested using the system recommended by Strauss and Corbin. Classification schemes and typologies will be used to identify and develop themes and concepts emerging from the data. Once coding has been completed and thematic and conceptualmaterial developed, we will also use descriptive data analysis to examine the importance and intensity of categories by their repetition within and across interviews, using counts and frequencies.

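### The H4 cost model names neither the randomization blocks nor the collected pre-index cost: a cheap gain in precision and calibration is left unused, without bias

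*Combined protocol and SAP*

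**What the plan says.** **Randomization.** The Overview of Study Implementation Process and Design describes "34 primary care clinics blocked on size and Essentia geographic service area". The number of blocks is not given. Study Sites reports an average of "14 PCPs (range: 1-56) and 377 prediabetes patients at high CV risk per clinic", so clinics differ widely in size.

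**H4.** Aim 2 Analytic Approach estimates annualized cost by arm with a GEE, typically gamma with a log link, clustered by clinic and "controlling for demographics, time, and baseline clinical risk factors". It states no working correlation, standard error estimator or reference distribution. Under Aim #2 – Health Care Costs (H4), the costs collected are those "incurred prior to and up to a 24-month post-index date period by participants in each study group". Pre-index cost is therefore held, but its role in the model is not stated.

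**Aim 1 model.** For rate-of-change outcomes, Aim 1 Analytic Approach lists "fixed effects for clinic-randomized treatment group, years elapsed since index CVR, the treatment by years elapsed interaction and the index outcome value", with random clinic and patient intercepts. Blocks are not listed.

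**Optional adjustment.** Measures of Covariates says: "Patient or provider characteristics may also be used to adjust for covariate imbalance introduced by clinic randomization". This is permissive, and it names neither clinic size nor service area.

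**H3.** Definition and Measurement of Variables says "H3 will be supported if appropriate drug use improves over the follow-up period" in the CDS clinics relative to usual care. Aim 1 Analytic Approach says "the treatment group parameter is expected to estimate more appropriate pharmacologic use among patients in CDS compared to UC clinics". The first can be read as a test of change over time; the second is a treatment main effect.

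**The concern.** H4 compares arms between 34 randomized clinics. Blocking on factors that predict cost removes their variance from the true sampling error of the arm contrast. A model without the blocks leaves that variance in the standard error, so the stated precision does not match the design. Baseline cost is often among the better predictors of later cost. If it is not a covariate, precision may be lost; if it is a repeated outcome reached through the time term, the estimand differs. The plan does not say which applies.

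At stake is some power for H4, and for H3 if it is a main-effect test, together with the calibration of an H4 test built on 34 clusters. H1 and H2 are tested by the treatment-by-time parameter in a model with random intercepts only, where block main effects do little.

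**Working it through.** **The plan's own figure.** There is none for H3 or H4. The only power calculation is for H1 (section 2.2.6.1), and it supplies the clinic ICC range of .001 to .02.

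**Inputs.** From the documents: 34 clinics and 6,600 analysis patients, so m = 6,600/34 = 194 per clinic. Assumed: the H1 ICCs carry over to cost, 6 strata, 1:1 allocation within strata, and blocks explaining R = 30% of clinic variance beyond the model covariates.

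**Step 1, closed form.** The clinic-level share of the arm-contrast variance is c = mρ/[1+(m−1)ρ]. The share due to blocks is f = R·c. If the block-adjusted test has 80% power, the test without blocks has size 2[1−Φ(1.96/√(1−f))] and power Φ(2.80−1.96/√(1−f)).

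| ICC | c | f | size | power | loss (points) |
|---|---|---|---|---|---|
| .001 | .163 | .05 | .044 | .786 | about 1.5 |
| .005 | .494 | .15 | .034 | .751 | about 5 |
| .02 | .798 | .24 | .025 | .710 | about 9 |

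This treats the standard error as well estimated. With 34 clusters, an ordinary sandwich is not.

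**Step 2, simulated power.** Linear clinic-mean model, R = 30%.

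| Test | ICC .001 | .005 | .02 |
|---|---|---|---|
| No blocks, ordinary sandwich, z | .818 | .792 | .766 |
| No blocks, corrected SE, t | .778 | .755 | .717 |
| Blocks, corrected SE, t | .791 | .789 | .794 |

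Against the corrected test without blocks, the gain is 1.3, 3.4 and 7.7 points. Against the uncorrected one, the net change is −2.7, −0.3 and +2.8. A separate linear run (6,000 replicates) gave −3.3, −0.2 and +3.0. A gamma log-link GEE (3,000 replicates), with both tests corrected, gave .811 vs .809, .805 vs .778 and .825 vs .746, that is 0.2, 2.7 and 7.9 points. The Monte Carlo error of one power figure there is about √(.8×.2/3000) = .007.

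**Step 3, size (gamma GEE, R = 30%; ICC .001/.005/.02).**
- No blocks, ordinary sandwich, z: .063/.050/.041.
- No blocks, corrected SE, t: .049/.034/.030.
- Blocks, ordinary sandwich, z: .095/.085/.093.
- Blocks, corrected SE, t: .048/.045/.055.

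The uncorrected sandwich is liberal and the omitted blocks are conservative. The two roughly cancel in the middle of the ICC range. Adding blocks without the correction makes matters worse.

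**Step 4, sensitivity.**
- R = 10%: gain over the equally corrected test −0.3, 0.8 and 1.7 points.
- R = 50%: the same gain is 0.1, 6 and 16 points. Net of the uncorrected test it is about −2, +3 and +10.
- R = 0: adding blocks costs 0.3 to 1.6 points.
- Unequal clinics (21 to 777 patients, R = 30%), blocks with corrected SE and t: size .059/.059/.069 under working independence and .054/.051/.049 under exchangeable correlation.

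**Step 5, pre-index cost.** Assume equal variance and ICC for pre- and post-index cost, patient-level correlation r, clinic-level correlation r_c, and one common slope r. The arm-contrast variance is multiplied by c(1+r²−2r·r_c) + (1−c)(1−r²). With r = .6 and ICC .02 (c = .798):
- r_c = .8: .798×.40 + .202×.64 = .448, so about 55% is removed.
- r_c = 0: .798×1.36 + .202×.64 = 1.214, so the variance rises by about 21%.

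Neither correlation is in the documents.

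**The case against.** The strongest objection concerns the comparator. The plan says only that clustering by clinic is allowed for. If that means an ordinary sandwich with a normal reference, the proposed analysis does not gain power at every ICC: at R = 30% it is about 3 points lower at ICC .001 and level at .005. At R = 10% it is lower throughout (.797/.791/.800 against .831/.819/.821). This stands as arithmetic. At low ICC, and at R = 10%, part of that advantage comes from a size above 5% (.055 to .068), so it is not a reason to prefer the uncorrected test. At R = 30% and ICC .005, the two tests are simply equivalent.

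Four further points stand in part:
- Demographics and baseline risk factors may already absorb some of the block effect, so the relevant R is residual and may be small.
- The optional adjustment clause shows that imbalance was considered, though it does not name the blocks.
- The Aim 1 list of fixed effects is written for rate-of-change outcomes. Its use for H3 is an inference, and the index outcome value might absorb block differences there too.
- The time term in the cost model could mean a pre/post period, with pre-index cost entering as an outcome. The text does not say so.

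**Conclusion.** The omission is real and its consequence is modest. H4 can be made more precise and better calibrated with variables that should already be held. Under the stated assumptions, blocks add about 0-1, 3-4 and 8 points against an equally corrected test, and about −3, 0 and +3 net of an uncorrected one. At R = 50% and ICC .02, the net gain is about 10 points. Block count, block strength, cost ICC and standard error method are all unstated, so no single figure belongs to the plan.

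A reader might infer more, and the documents do not support it:
- *The H4 estimate is biased, or the primary result is weakened.* Randomization protects the estimate, and H1 and H2 rest on slopes.
- *The plan forfeits 8 points of power.* That holds only at ICC .02 and only against a corrected test without blocks, which the plan does not specify.
- *The H4 test is conservative as written.* With an uncorrected sandwich it may be slightly liberal at low ICC.
- *A ceiling can be put on the gain from pre-index cost.* Step 5 shows that it depends on an unknown clinic-level correlation.
- *H3 is affected.* That depends on which of two inconsistent descriptions governs.

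**What to change.** 1. **Aim 2 model.** State that post-index cost is the outcome. Add annualized pre-index cost and the blocking factors (size stratum, service area) as covariates.
2. **Inference, in the same change.** Use a small-sample corrected clinic-level sandwich (for example Kauermann-Carroll) and a t reference with df equal to 34 minus the number of clinic-level parameters. Name the working correlation. Do not add blocks without this.
3. **H3.** First reconcile Definition and Measurement of Variables with Aim 1 Analytic Approach on which parameter decides H3. Add the blocks only if it is the treatment main effect.

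**Cost.** Wording in one model paragraph, or two if H3 is included. Six strata would move the clinic-level df from 32 to 27 (critical value 2.04 to 2.05). If the blocks are not prognostic, about 0.3 to 1.6 points of power are lost. The note on Hypothesis 5 shows that efficacy results were known when this version was written. If H3 or H4 results are known too, report the adjusted models as supportive analyses.
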